- Age-appropriate questionnaire for palatability/acceptability of berotralstat oral granules as assessed by the site following the first dose

Methodology:

This is a single-arm, open-label study designed to evaluate the PK of berotralstat; plasma concentrations of berotralstat will be measured and used in population PK analyses, allowing for determination of the appropriate weight-based dose for pediatric patients 2 to < 12 years old. In addition, the safety and tolerability of berotralstat will be assessed when given to pediatric subjects who are 2 to < 12 years old as a prophylactic treatment to prevent attacks of HAE. The effectiveness of berotralstat in this population will be summarized using descriptive statistical methods. Subjects will be enrolled into 4 or more dose cohorts; subject weight will be used to determine assignment to each cohort with the higher weight cohorts (Cohorts 1 and 2) enrolling first and in parallel. Cohort 3 will open for enrollment and initiate the 12-week standard-of-care (SOC) phase after ≥ 4 subjects from Cohorts 1 and 2, with ≥ 2 of the subjects from Cohort 2, have reached Week 2. Cohort 4 will open for enrollment and initiate the 12-week SOC phase after ≥ 4 subjects in Cohort 3 have reached Week 2. BioCryst will notify sites when Cohorts 3 and 4 are open for enrollment. Safety assessments by the Data Monitoring Committee (DMC) and PK modelling from all available PK data to confirm the weight band for the cohort will occur prior to dosing subjects in Cohorts 3 and 4 with berotralstat. Additional dose cohort(s) may be enrolled if indicated based on safety and/or population PK analyses with DMC endorsement.

This study will consist of 2 treatment periods: a 12-week SOC treatment period followed by an open-label berotralstat treatment period lasting up to 144 weeks. The berotralstat treatment period is divided into 3 parts as defined below. Throughout the study, site personnel will monitor subject safety through a combination of in-person clinic visits and tele-communication with the parent/caregiver(s) (P/C). The tele-contact may be either a telephone call or telemedicine visit conducted over the internet.

The study schema is as follows:

Abbreviations: BSLN = Baseline; DC = discontinue; Enr = enrollment; P/C = parents and/or caregivers; PK = pharmacokinetic; QD = once daily; SOC = Standard of Care; Wk = Week.

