Part 3: After Week 48, subjects may continue to receive open-label berotralstat in Part 3 (Weeks 48 through 144; a total of 96 weeks). Visits in Part 3 will occur every 24 weeks: Weeks 72, 96, 120, and 144. Also during Part 3, sites will contact the P/C at 12-week intervals between study visits (ie, at Weeks 60, 84, 108, and 132) to assess the subjects' overall wellbeing. The contact should be an arranged tele-contact; however, it may become an on-site visit if the investigator or P/C considers an in-person visit necessary for medical management of the subject. Berotralstat will be provided in Part 3 through Study Week 144 or until another mechanism is available to provide drug to the subject (eg, market access, separate study) or the sponsor discontinues development of the product for the prevention of angioedema attacks in children < 12 years of age.

Subjects who discontinue berotralstat at Week 144 or earlier will be required to attend an end-of-study (EOS) follow-up visit 3 weeks after study drug discontinuation. Subjects who discontinue the study but

will continue to receive berotralstat via another mechanism will have EOS assessments performed at their last regularly scheduled visit.

PK Assessments: At Week 2 in Part 1, plasma samples for PK analysis will be collected immediately prior to dosing and at designated timepoints post dose. Based on the PK results, the dose regimen of berotralstat may be adjusted for an individual subject or for all subjects in the cohort to ensure exposures fall within the acceptable safety range; the dose of berotralstat will not be adjusted based on changes to the subject's weight during Part 1. In Part 2, one random sample for PK analysis will be drawn at Weeks 12, 24, 36, and 48. Reduced PK sampling may be performed in smaller subjects, especially subjects in Cohort 4, to maintain blood sample volumes within acceptable ranges.

Additional PK samples should be drawn if the berotralstat dose is adjusted.

Number of subjects (planned):

Approximately 30 subjects are planned to be enrolled.

Main criteria for inclusion:

- Age 2 to < 12 years of age and weighing ≥ 12 kg
- Parent/caregiver willing and able to provide written, informed consent (with assent from the child where appropriate).
- Subjects with a clinical diagnosis of HAE. A clinical diagnosis of HAE is defined as:

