9. STUDY CONDUCT

9.1. Schedule of Assessments

The study schedule of assessments is shown in [Table 2](#); study procedures are described in Section [10](#).

Table 2: Schedule of Assessments

Assessment	Standard-of-Care Therapy			Open-label Berotralstat Treatment											Post Treatment Follow-Up
				Part 1					Part 2 (Wks)		Part 3 (Wks)			EOS Visit ^a	
	Scr./Enr. ^b	Wks 4 & 8 ± 1Wk	Washout [prior to Day 1]	Baseline (Day 1) ^c ± 4 days	Wk 2 +4 days	Wk 6 ± 3 days	Wk 9 ^d ± 1 Wk	Wk 12 ± 3 days	16, 20, 28, 32, 40, 44 ±1 Wk	24, 36, 48 ± 1 Wk	60, 84, 108, 132 ± 1 Wk	72, 96, 120 ± 1 Wk	Wk 144 ± 1 Wk	3 wks (± 3 days) after the last dose	
Informed consent ^c	X														
Inclusion-exclusion criteria (including confirmation of C1-INH HAE diagnosis)	X			X ^f											
Medical and medication history	X			X											
Weight/height/BMI ^g	X			X	X	X		X		X		X	X	X	
Physical examination ^h	X			X	X	X		X		X		X	X	X	
Vital signs ⁱ	X			X	X	X		X		X		X	X	X	
Clinical chemistry/hematology ^j	X			X	X	X		X		X			X	X	
Urinalysis ^k	X			X	X	X		X		X			X	X	
Pregnancy testing ^l	X			X		X		X		X		X	X	X	
Discontinuation of therapy ^m • Oral androgen ⁿ • CYP2D6 or CYP3A4 substrates • ACE-inhibitor • Lanadelumab • SOC prophylaxis ^o			≥ Day -28 ≥ Day -7 ≥ Day -7 ≥ Day -28 ≥ Day -1												
ECG ^{p,q}	X			X	X	X		X		X			X	X	
Telephone/telemedicine contact ^r		X ^s					X		X ^t		X ^t				
PK: single, random plasma sample ^u								X		X					
PK: multiple samples ^v					X										
Diary instructions and/or review ^w	X	X		X	X	X		X	X	X					

Assessment	Standard-of-Care Therapy			Open-label Berotralstat Treatment										Post Treatment Follow-Up
				Part 1					Part 2 (Wks)		Part 3 (Wks)			
				Clinic Visits and Contact					Site Contact	Visits	Site Contact	Visits	EOT	EOS Visit ^a
	Scr./ Enr. ^b	Wks 4 & 8 ± 1Wk	Washout [prior to Day 1]	Baseline (Day 1) ^c ± 4 days	Wk 2 +4 days	Wk 6 ± 3 days	Wk 9 ^d ± 1 Wk	Wk 12 ± 3 days	16, 20, 28, 32, 40, 44 ±1 Wk	24, 36, 48 ± 1 Wk	60, 84, 108, 132 ± 1 Wk	72, 96, 120 ± 1 Wk	Wk 144 ± 1 Wk	3 wks (± 3 days) after the last dose
HAE therapy														
• Standard of care (SOC)	X	X												
• Berotralstat				X	X	X	X	X ^x	X	X	X	X	X	
Palatability/acceptability assessment ^y				X										
Adverse events	X	X		X	X	X	X	X	X		X	X	X	X ^z
Concomitant medications	X			X	X	X	X	X	X	X	X	X	X	X

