10.4. Weight/Height/Body Mass Index

Subject weight is important for this study as the dose of berotralstat will be based on subject weight. Therefore, the site should be diligent in accurately taking and recording subject weight. Subjects should be weighed in light clothing with shoes and other heavier items (eg, belts or phones) removed. Heavier outer clothing (eg, jackets or sweaters) should also be removed.

Height should be recorded at the indicated visits. Body mass index (BMI) should be calculated at all visits where weight and height are measured using the following formula:

$$\text{BMI} = \text{weight (kg)} / \text{height (m)}^2$$

10.5. 12-lead Electrocardiograms

A standard bedside or routine 12-lead ECG machine that calculates heart rate and measures the PR, QRS, QT, RR, and QTc intervals will be used. Prior to obtaining an ECG, subjects should rest quietly for at least 10 minutes. Resting may be in a supine position or other position (eg, on the P/C's lap) as age appropriate for the subject.

Qualified site personnel should review the ECGs and automated findings in real time for gross abnormalities and interval measurements of concern (absolute readings and for post-baseline ECGs, a change from baseline). For all ECGs, the clinical interpretation of the ECG and calculated QTc should be recorded directly on a hard copy of the ECGs. Copies of the ECGs may be requested by the sponsor. All subject identifiers will be masked prior to provision to the sponsor.

Baseline (pre-dose) ECGs will be obtained in triplicate (ie, 3 separate readings taken at 1- to 5-minute intervals) with baseline values calculated from an average of the 3 readings. All other ECGs will be single assessments.

An ECG should be repeated for a change from baseline in QTc > 60 msec or a QTc interval > 500 msec.

If AEs commonly associated with prolonged QTc interval (eg, unexplained intermittent or continuous lightheadedness, syncope, palpitation, chest pain) are reported or the dose is modified, additional ECGs should be recorded. ECGs obtained due to dose modification should be taken approximately 2 to 6 weeks after dose modification and should be aligned with PK blood sample timelines described in Section 10.9.1 to the extent possible.

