12.2.2. General Considerations for Data Analysis

Descriptive statistics will be used to summarize the data from this study. Data will be summarized by cohort, overall, and by study day or time, if appropriate. Unless stated otherwise, the term “descriptive statistics” refers to number of subjects (n), mean, standard deviation (SD) or standard error of the mean (SEM), median, minimum, and maximum for continuous data, and frequencies and percentages for categorical data. For TEAE data, both the number of subjects and total number of events will be reported. For PK endpoints, please see Section [12.2.4](#) for further details.

Data summaries will be provided to the DMC as specified in the DMC Charter. Interim analysis of PK, safety, and effectiveness data may be conducted after at least 15 subjects complete

48 weeks of treatment (Part 2) and/or after all subjects complete 48 weeks of treatment. Additional interim analyses may be performed during the course of the study as needed to support regulatory filings, safety updates, and publications, as documented in the SAP. Effectiveness data are not collected after Week 48. Disposition and safety data will be summarized through the end of study (Week 144).

The final analysis of disposition, dosing, and safety data collected in Parts 1, 2, and 3 will be conducted once the last subject completes or discontinues his or her respective parts, the resulting clinical database has been cleaned and quality checked, the analysis populations have been finalized, and after database lock has occurred. Disposition, dosing, and safety data will be summarized through the end of study (Week 144).

Data collected during the study will be included in data listings as measured or recorded in patient diaries. Unless otherwise noted, data listings will be sorted by subject and study visit/date.

Statistical analyses will be conducted using SAS® software version 9.2 or higher (SAS Institute, Cary, North Carolina, US). All analyses will be subject to formal verification procedures. All tables and figures generated to summarize data will be reviewed by the lead statistician to ensure accuracy and consistency of analyses; the lead clinical pharmacologist will review data summarized for the PK endpoints to ensure their accuracy and consistency.

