6.8.1. Multiple Assessments

Where multiple scheduled measurements are recorded for a given time point (ie, triplicate ECGs or repeated blood pressure assessments), the mean of the measurements will be calculated and used in any derivation of summary statistics. All available data will be listed.

When multiple visits occur within the same window, the scheduled visit will be used in the analysis if available. If no scheduled visit occurs within the window and unscheduled visit(s) and/or an early termination visit occur within the window, the analysis visit closest to the target day will be selected for use in analysis. If deemed appropriate by the sponsor (eg, in the case of a

retest), unscheduled visits may be chosen for analysis given documentation of the desired visit from the sponsor.

Results from unscheduled visits will be eligible for inclusion in analyses of worst post-baseline results regardless of their use for 'by visit' displays.

Listings will display all visits as recorded on the eCRF, including the date and study day. All available data including any totals, domains, or subscales of scale assessments summarized will be listed.

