11.3.1. Analysis of Abnormal Laboratory Values

Laboratory abnormalities will be graded according to the DAIDS (also see Section 6.7.6). Treatment-emergent graded toxicities are defined in Section 6.7.6 (including exceptions) and the number and percentage of subjects who experience treatment-emergent graded toxicities will be summarized by panel, parameter, time point, and cohort.

Laboratory toxicity shifts from baseline to worst post-baseline grade will be summarized by panel, parameter, toxicity grade, and cohort.

The following categories of abnormal hepatic laboratory values will be evaluated for any occurrence among all post baseline assessments (where “and” indicates elevations occurring at the same visit). Within each treatment group and laboratory parameter grouping, a subject may be counted once per elevation criteria using the worst-case result. That is, a subject with a worst-case alanine transaminase (ALT) elevation $>3 \times$ the ULN for a given treatment group would be counted once in the ALT $> 1.5 \times$ ULN category and once in the ALT $> 3 \times$ ULN

category, regardless of how many ALT elevations the subject had that met the $> 3 \times \text{ULN}$ and $> 1.5 \times \text{ULN}$ elevation criteria.

- ALT and/or aspartate transaminase (AST) $> 3 \times \text{ULN}$ and total bilirubin > 1.5 or $2 \times \text{ULN}$
- AST $> 1.5, 3, 5, 10,$ and $20 \times \text{ULN}$
- ALT $> 1.5, 3, 5, 10,$ and $20 \times \text{ULN}$
- Total bilirubin $> 1, 1.5,$ or $2 \times \text{ULN}$
- Alkaline phosphatase (ALP) $> 1.5 \times \text{ULN}$

Profiles of liver enzymes and bilirubin over time will be graphically displayed for subjects with any Grade 3 or 4 abnormality in these analytes. In addition, a listing of all liver function test (ALT, AST, bilirubin, ALP, gamma-glutamyl transferase) results for subjects experiencing a treatment-emergent Grade 3 or 4 liver function test will be provided.

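### After Week 48 only one on-drug laboratory and ECG panel is scheduled, at Week 144, and the SAP's denominator, window and worst-grade rules do not allow for this in the final safety tables

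*SAP*

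**What the plan says.** **Schedule.** The synopsis describes an "open-label berotralstat treatment period lasting up to 144 weeks", of which Part 3 is "Weeks 48 through 144; a total of 96 weeks". It adds that "Visits in Part 3 will occur every 24 weeks: Weeks 72, 96, 120, and 144". In Protocol Table 2 (Section 9.1) the row "Clinical chemistry/hematology" is marked at screening, Day 1, Weeks 2, 6, 12, 24, 36, 48 and 144, and the end-of-study (EOS) visit. It is blank at Weeks 72, 96 and 120. The urinalysis and ECG rows follow the same pattern. Weight, vital signs, examination and pregnancy testing are marked at Weeks 72, 96 and 120. The SAP's copy of the schedule agrees.

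**Other sources of Part 3 values.** A child who leaves during Part 3 completes the Week 144 assessments (Protocol 9.5.3). A child who stops drug also attends EOS three weeks later, and one who moves to another supply of drug has EOS assessments at the last regular visit (9.6). On extra ECGs, Protocol 10.5 says "ECGs obtained due to dose modification should be taken approximately 2 to 6 weeks after dose modification". Weight-based dose changes continue through Part 3 (Table 2, footnote x).

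**Analysis.** SAP 5.2 summarizes safety through Week 144. SAP 11.3.1 gives treatment-emergent toxicity by time point and states that "Laboratory toxicity shifts from baseline to worst post-baseline grade will be summarized by panel, parameter, toxicity grade, and cohort". SAP 11.5 gives QTcF categories by time point. Table 7 marks the shift tables, liver-test plots, QTcF categories and the QTcF, PR and QRS plots for the final analysis. SAP 6.4 makes the cohort total the default percentage denominator. SAP 6.8 leaves unscheduled and early-termination visits out of by-visit displays. SAP 6.8.1 says that if a window holds no scheduled visit but does hold such a visit, "the analysis visit closest to the target day will be selected for use in analysis".

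**The concern.** The final outputs put Weeks 1 to 48 and Weeks 48 to 144 on one footing, although routine testing nearly stops after Week 48. Three rules then matter.

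- **Denominator.** SAP 11.3.1 and 11.5 name no denominator for toxicity and QTcF categories by time point, so the SAP 6.4 default applies. A child with no value at a time point stays in the denominator and is read as having no abnormality.
- **Window filling.** SAP 6.8 and 6.8.1 give opposite instructions for unscheduled values. Under 6.8.1, any Part 3 point before Week 144 would be a selected sample: children tested because of an event, a dose change or leaving.
- **Pooling.** One worst post-baseline grade over the whole study does not show which period was searched closely and which was not.

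At stake is what can be said about long-term laboratory and ECG safety in young children. The dose can change with weight throughout Part 3, and Protocol 4.4.5 records a label warning on QT prolongation at higher doses.

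**Working it through.** **1. Inputs.** Treatment lasts up to 144 weeks, and Part 3 takes 96 of them (synopsis). Scheduled on-drug panels fall at Weeks 2, 6, 12, 24, 36, 48 and 144 (Protocol Table 2). About 30 children are planned (Protocol 12.1).

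**2. The plan's own figure.** Protocol 12.1 gives about a 96% chance that 30 children show at least one event of 10% incidence. 1 − 0.9^30 = 0.958, so it is reproduced. It assumes that every event is seen when it happens.

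**3. Testing density.**
- Part 3 share of maximum treatment: 96/144 = 66.7%.
- Intervals between on-drug panels, from Day 1: 2, 4, 6, 12, 12, 12 and 96 weeks. With ±1-week windows at Weeks 48 and 144, the last is 94 to 98 weeks.
- Panels per 12 weeks: Weeks 1 to 48, 6/48 × 12 = 1.5; Part 3, 1/96 × 12 = 0.125. The ratio is 12.

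**4. What one panel can find.** Assume an abnormality starts uniformly over Weeks 48 to 144 and lasts D weeks, and that nothing prompts an earlier test. The Week 144 panel catches it if it starts in the last D weeks, so the capture probability is c = D/96. The EOS panel at Week 147 adds nothing here, because an abnormality that starts before Week 144 and is present at Week 147 is also present at Week 144. If such an abnormality arises in 10% of children during Part 3 and all 30 reach Week 144, the chance of seeing at least one case is 1 − (1 − 0.1c)^30.

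| D (weeks, assumed) | c | Chance of at least one case among 30 |
|---|---|---|
| 4 | 4.2% | 11.8% |
| 8 | 8.3% | 22.2% |
| 12 | 12.5% | 31.4% |
| 24 | 25.0% | 53.2% |

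The 95.8% of step 2 is the comparison. Lasting or symptomatic abnormalities would be found more often than the table shows.

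**5. Denominator.** With N children in a cohort, m tested at a time point and x of them abnormal, the SAP 6.4 default gives x/N, while the tested children give x/m. The reported figure is too low by the factor m/N. As an illustration only: in a cohort at the minimum size of 4, with 2 tested and 1 abnormal, the table shows 1/4 = 25% instead of 1/2 = 50%.

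**6. The two visit rules.** SAP Table 4 has windows at Weeks 60 to 132. Under SAP 6.8 no laboratory or ECG point appears in them. Under 6.8.1, unscheduled or early-termination values may fill them. At Weeks 72, 96 and 120 a scheduled visit does take place, but without laboratory tests or ECG, and 6.8.1 does not say whether its condition refers to the visit or to the assessment. Two programmers could produce different tables.

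**The case against.** The strongest reply is that the schedule is open and deliberate. Protocol 5.2.2 and SAP 3.2.2 place safety assessment at Weeks 12, 48 and 144 or EOS, all analysis is descriptive, and no passage calls the final percentages a 144-week incidence. This stands: the sparse testing does not contradict the SAP, and the point is only how its results are tabulated.

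Second, SAP 5.1 and Table 7 already plan the same outputs on data through Week 48. That is so, but the analysis is optional, and the final tables themselves are not split. Table 7 does split serious adverse events by Part, so the format exists.

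Third, SAP 6.2 requires tables to show how many subjects the data apply to, and continuous summaries give the number with data (6.4). Sparse data would therefore be partly visible, but the percentage denominator would not change. The table shells are in a separate document and might settle it; the SAP text does not.

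A reader might infer more than the documents support:

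- *No laboratory test at all after Week 48.* Urine pregnancy tests are scheduled at Weeks 72, 96 and 120 for girls of childbearing potential.
- *All values between Week 48 and Week 144 come from adverse events or dose changes.* Leavers have full panels, and some ECGs follow dose changes caused only by growth.
- *The worst-grade percentage would fall with longer follow-up.* It is cumulative on a fixed population and cannot fall. Only by-time-point percentages can.

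**Conclusion.** The point holds as an analysis weakness that the SAP should correct. For a child who reaches Week 144, the last 96 of 144 treatment weeks carry one scheduled on-drug panel against six in the first 48, plus an off-drug EOS panel if drug is stopped. For children who leave earlier, the gap is shorter. Under the SAP as written, untested children count as free of abnormality in by-time-point percentages, Part 3 points before Week 144 depend on which of two conflicting rules is followed, and a pooled worst grade hides the change in testing. Few new abnormalities in Part 3 would say little: capture is 4.2% to 25% for durations of 4 to 24 weeks.

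The schedule counts are read directly from Protocol Table 2. The capture figures rest on the assumed duration, a uniform start and no earlier prompted test. The denominator point assumes that the separate shells do not override SAP 6.4.

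**What to change.** For the final analysis, amend SAP 6.8, 6.8.1, 11.3 and 11.5:

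1. For toxicity and QTcF category percentages by time point and for Part 3, use as denominator the number of children with a value at that time point or in that period, and print it.
2. Reconcile 6.8 with 6.8.1, so that by-visit tables and over-time plots for laboratory and ECG data use only time points with a scheduled assessment (Weeks 2, 6, 12, 24, 36, 48 and 144). List other Part 3 values separately.
3. Show worst post-baseline shift and treatment-emergent toxicity for Day 1 to Week 48 and for Part 3 separately, both against the Day 1 baseline. A footnote should give the scheduled on-drug panels in each period (six and one) and say that an abnormality lasting across Week 48 counts in both.

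The cost is SAP wording, a few more table columns and smaller Part 3 denominators. No new data or visits are needed.

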11.3.2. Complement Factors and HAE Diagnosis

Laboratory results related to HAE diagnosis, including complement factors C1-INHA_g, C1-INH_f, and C4 will be included in summaries of laboratory data. Criteria used to confirm diagnosis of HAE Type I or II will be summarized and listed as described in Section 9.6.

